7.0 Removal of Subjects in the Study

A subject may be discontinued from the study at any time if the subject, or investigator determines that it is not in the best interest of the subject to continue participation. A subject who prematurely discontinues treatment will be asked to return for a follow-up visit approximately 4 weeks following administration of the last dose of ivacaftor.

A subject will be discontinued from the study for any of the following reasons:

- A female subject has a confirmed pregnancy or, in the case of a male subject, his female partner becomes pregnant.
- A subject experiences an arrhythmia or conduction abnormality including, but not limited to, prolonged QTcF interval, where the severity is categorized as CTCAE version 4.0 Grade 3 or higher.
- A subject experiences MI/unstable angina or stroke/Cerebrovascular accident

A subject experiences

- an elevated alanine transaminase (ALT) or aspartate transaminase (AST) of $>8 \times \text{ULN}$ or
- ALT or AST $>5 \times \text{ULN}$ for more than 2 weeks or
- total bilirubin $>2 \times \text{ULN}$ and/or clinical jaundice, in association with elevation of ALT or AST $>3 \times \text{ULN}$ and no convincing alternative etiology (e.g., viral hepatitis, alcohol ingestion) for the Elevated transaminase is identified, regardless of whether ALT or AST levels had improved

A subject may be discontinued from the study for any of the following reasons:

- A subject develops a medical condition that requires prolonged concomitant therapy with a prohibited medication.
- A subject experiences a prolonged interruption of study drug.
- A subject develops a life-threatening adverse event, or a serious adverse event (SAE) that places them at immediate risk.
- A subject is noncompliant with study requirements.

- A subject experiences an increase in liver function tests (LFTs) to $3 \times$ ULN (if the baseline LFTs are normal) or an increase that exceeds an absolute value of $5 \times$ ULN

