6.0 Statistical Analysis Plan

Safety analysis will be conducted by descriptive statistics. Pharmacodynamic analysis will be evaluated within group for the ivacaftor treatment group for changes between screening/day 1 and day 84. We will also compare findings between groups. The primary outcome measure is safety; the primary efficacy outcome measure is MCC (AUC₆₀) and change in FEV1 (% predicted). Secondary outcome measures including change in other measures of spirometry, PROs, exacerbation frequency, and 6MWD will also be analyzed. These data will be used to test the null hypothesis of no change using a paired t-test unless the distributions are notably skewed, in which case the non-parametric Wilcoxon signed-rank test will be implemented. Between group comparisons and composite time-dependent changes based on multiple measures (e.g. sweat chloride, MCC, FEV1, etc.) will be conducted as secondary analyses using the two-group t-test (or the non-parametric Wilcoxon rank-sum test if needed) and analysis of covariance models. The dose groups will be compared simultaneously using analysis of variance (or the nonparametric Kruskal-Wallis test if needed). Longitudinal analyses will consist primarily of mixed models repeated measures analyses. An appropriate structure for the covariance matrix will be selected for these models using the final data. When a model term is statistically significant, the Tukey-Kramer multiple comparisons test will be used to determine which specific pairs of means are significantly different. Interaction terms may be included in some models. All statistical tests will be two-sided and will use $\alpha=0.05$. Power analysis for measurements of MCC, CFTR function measured by sweat chloride, and FEV1 (% predicted) are provided below. The off drug effect will be measured by using data from the follow-up visit to assess the change from on drug to washout at the follow up visit.

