9.1 Role of Vertex IIS regarding provision of study drug and placebo

- Vertex Pharmaceuticals will provide ivacaftor and matching placebo to randomize up to approximately 50 subjects to achieve approximately 40 completers (35 active patients and 15 placebo treated patients for 84 days, assuming 5 dropouts in the ivacaftor group and 5 dropouts in the placebo group). This will provide sufficient compound for lost samples, if they occur.

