16.8 Elevation of Liver Function Test Parameters

Subjects with new ALT or AST elevations of $>3 \times$ ULN and clinical symptoms be followed closely, including repeat confirmatory testing within 48 to 72 hours of the initial finding and subsequent close monitoring of ALT and AST level, as clinically indicated.

Study drug administration will be interrupted immediately and the DSMB Chair will be notified if any of the following criteria is met:

- ALT or AST $>8 \times$ ULN
- ALT or AST $>5 \times$ ULN for more than 2 weeks
- Total bilirubin $>2 \times$ ULN and/or clinical jaundice, in association with elevation of ALT or AST $>3 \times$ ULN

A thorough investigation of potential causes should be conducted and the subject will be followed closely for clinical progression.

If no convincing alternative etiology (e.g., viral hepatitis, alcohol ingestion) for the elevated transaminases is identified, regardless of whether ALT or AST levels have improved, the subject will be discontinued from the study, in consultation with the Medical Monitor

An early termination visit should be scheduled as soon as possible. In addition to the early termination visit assessments specified in the protocol, a blood sample should be obtained for pharmacokinetic analysis. Subjects discontinued for elevated transaminases should be followed until their transaminases normalize or return to baseline. If a convincing alternative etiology for the elevated transaminases is identified and the subject's symptoms and laboratory findings have improved, the investigator will consider resuming study drug treatment in consultation with the PI.

16.9 Definition of COPD Exacerbation.

We will monitor the incidence and severity of COPD exacerbations to measure safety of ivacaftor and estimate whether a reduction in COPD exacerbations is plausible with effective CFTR potentiation by ivacaftor, and to develop sample size estimates for future studies. For the purposes of this protocol, COPD exacerbations will be defined as follows: a complex of respiratory symptoms (increase or new onset) of more than one of the following: cough, sputum, wheezing, dyspnea, or chest tightness, requiring treatment with antibiotics and/or systemic steroids for at least three days.

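### Patients who stop study drug have no planned Day 28/56/84 assessments, and the lead paired efficacy test uses only those with a Day 84 value; assumed drop-out is also stated inconsistently

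*Combined protocol and SAP*

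**What the plan says.** **Stopping treatment.** Section 7.0 says: "A subject who prematurely discontinues treatment will be asked to return for a follow-up visit approximately 4 weeks" after the last dose. The medical events it lists lead to discontinuation from the study, not merely from study drug, and a prolonged interruption of drug is itself a possible ground for leaving. Section 16.8 asks for an early termination visit in liver-test cases, with a PK sample "In addition to the early termination visit assessments specified in the protocol". Table 1 has columns for screening, Day 1, Day 28, Day 56, Day 84 and follow-up, and none for early termination.

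**Analysis.** Section 6.0 examines the ivacaftor arm "for changes between screening/day 1 and day 84" and states: "These data will be used to test the null hypothesis of no change using a paired t-test", with the signed-rank test if the data are skewed. Between-group comparisons "will be conducted as secondary analyses using the two-group t-test", its rank-based counterpart and analysis of covariance. Longitudinal analyses are to use mixed models. No analysis set, intention-to-treat rule or missing-data method is given.

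**Measurements (Table 1).** Spirometry and sweat chloride are taken at every visit, and the questionnaires at every visit from Day 1. MCC is measured only at screening and Day 84, and the walk test only at Day 1 and Day 84.

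**Drop-out.** The note to Table 2 uses 27 active patients after a 10% loss. The supply text (synopsis and Section 9.1) has 35 active and 15 placebo patients, "assuming 5 dropouts in the ivacaftor group and 5 dropouts in the placebo group".

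**Follow-up timing.** It is about 4 weeks after the last dose in Section 7.0, 14 ± 7 days after it in the synopsis, and Day 98 ± 2 in Table 1.

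**The concern.** A paired test to Day 84 needs a Day 84 value. If patients who stop drug are not asked to attend at Day 84, the lead estimate describes those who stayed on to the end. Where stopping is linked to worsening or to adverse events, that group will look better than everyone assigned to ivacaftor. The paired test also ignores Day 28 and Day 56 FEV1, sweat chloride and questionnaire values that were collected before the patient stopped.

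Safety is the primary outcome, and the same patients lose scheduled laboratory tests and adverse-event queries. Table 1 marks safety labs at the follow-up visit as done only if indicated. A Day 84 value that was never recorded cannot be recovered later.

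**Working it through.** **1. The plan's own figures.** The note to Table 2 gives 30 × (1 − 0.10) = 27. Solving the exact (noncentral t) power of a two-sided paired t-test for the detectable difference, with n = 27 and alpha 0.05:

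| Endpoint (SD) | Recomputed, 80% / 90% power | Table 2 |
|---|---|---|
| MCC (7) | 3.92 / 4.54 | 3.9 / 4.5 |
| FEV1 (5) | 2.80 / 3.24 | 2.8 / 3.2 |
| Sweat chloride (4) | 2.24 / 2.59 | 2.3 / 2.6 |

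Table 2 reproduces, apart from 2.24 being shown as 2.3. The sizing therefore already removes drop-outs from the paired test.

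**2. Drop-out rates.** From the supply text: ivacaftor 5/35 = 14.3%, placebo 5/15 = 33.3%, overall 10/50 = 20%. Table 2 uses 10% for the active arm and states no placebo rate. In addition, 35:15 is 2.33:1, while the design is 3:1.

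**3. Bias from using completers only.** For one arm:

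completer mean − all-randomised mean = drop-out share × (completer mean − drop-out mean).

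The documents give no figure for the gap in brackets. I assume 5 FEV1 points, with a range of 2.5 to 7.5, the same in both arms. Five points equals the SD in Table 2, but that SD is within-subject reproducibility and is not evidence about drop-outs.

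| Assumed gap | Ivacaftor, 10% | Ivacaftor, 14.3% | Placebo, 33.3% | Placebo minus ivacaftor (supply figures) |
|---|---|---|---|---|
| 2.5 | 0.25 | 0.36 | 0.83 | 0.48 |
| 5 | 0.50 | 0.71 | 1.67 | 0.95 |
| 7.5 | 0.75 | 1.07 | 2.50 | 1.43 |

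At a gap of 5, the overstatement within ivacaftor is 0.50/2.8 = 18% of the detectable difference at 10% drop-out, and 0.71/2.8 = 25% at 14.3%.

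**4. Direction between arms.** Under the supply figures placebo is overstated more than ivacaftor, so the completer contrast understates ivacaftor's advantage by 0.95 points at a gap of 5. If both arms lose the same share with the same gap, the two errors cancel and the shift is zero.

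**5. Precision.** With SD 5, the FEV1 difference detectable at 80% power within ivacaftor is 2.65 points for 30 patients and 2.44 for 35. Between arms it is 5.25 for 30 v 10 and 4.41 for 35 v 15. Day 84 values from patients who stop drug would therefore add precision as well.

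**The case against.** Several points on the other side stand.

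- **The visits are not cancelled in so many words.** That patients who stop drug miss Day 28/56/84 is inferred from Section 7.0 treating them as leaving the study and from the absence of any other provision. It is an omission, not a stated rule. Sections 16.4 and 16.8 also allow interruption with resumption, so not every stop is permanent.
- **The mixed model is already in the plan.** It can use partial FEV1 data, so a reader who infers that every FEV1 analysis is restricted to completers goes too far. However, Section 6.0 gives the test of no change to the paired test and does not say which result leads if the two differ.
- **The 14% v 33% imbalance does not reach the lead test.** That test is within the ivacaftor arm. The imbalance comes from a drug-supply request and can affect only the secondary between-group comparison, where the illustrated error runs against ivacaftor. The documents do not support the inference that unequal drop-out flatters the drug.
- **Safety follow-up is reduced, not absent.** The visit at about 4 weeks remains. Section 16.1 follows drug-related events still continuing at follow-up, and Section 16.8 follows liver cases until their values normalise or return to baseline.
- **Off-drug values change the question.** In a small pilot, the effect while taking the drug is a legitimate target. This is a reason to flag off-drug values, not a reason to leave them uncollected.

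**Conclusion.** The point holds in this form: no Day 28/56/84 assessment is provided after stopping drug, there is no analysis set or missing-data rule, and the lead paired test depends on having a Day 84 value. For MCC this dependence is complete, because the only post-baseline scan is at Day 84.

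With an assumed gap of 5 FEV1 points (2.5 to 7.5), the change within ivacaftor is overstated by 0.5 points (0.25 to 0.75) at 10% drop-out, or 0.7 (0.4 to 1.1) at 14%. The secondary contrast shifts by about 1.0 point (0.5 to 1.4) against ivacaftor under the supply figures, and by none if drop-out and gap are equal across arms. These are illustrations: both the size and the sign of the gap are assumed.

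The documents also disagree with themselves on assumed drop-out, on follow-up timing after the last dose, and on whether an early termination visit exists. A change should be made, but the plan is not invalid without it.

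**What to change.** 1. **Section 7.0.** Separate stopping study drug from withdrawing from the study. Ask patients who stop drug and agree to keep the scheduled spirometry, sweat chloride, questionnaire, laboratory and adverse-event assessments. No extra MCC scan is requested.
2. **Section 6.0.** Make the mixed model, on all randomised patients with any post-baseline value, the main analysis of FEV1 change at Day 84. It can still give the change within the ivacaftor arm. Flag each value as on-drug or off-drug so that both results can be reported, and keep the completer paired test as a sensitivity analysis. State the missing-data assumption: the model uses the earlier values but does not by itself remove bias if drop-out depends on values never observed.
3. **MCC.** State that the MCC result remains conditional on having a Day 84 scan.
4. **Reconcile** the drop-out figures (10% v 14% and 33%), the three statements of follow-up timing, and the early termination visit in Section 16.8 with Table 1.

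**Cost.** Protocol and SAP wording, plus some already scheduled visits for about 5 to 10 patients (10% of 50 = 5; the supply text has 5 + 5 = 10).

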8.0 Lost to Follow-Up

Subjects will be considered lost to follow-up if the following occurs:

- A subject misses 2 consecutive study visits.
- A subject is unable to be contacted by telephone subsequent to the 2 consecutive missed visits (3 documented attempts by telephone within 2 weeks following the second missed visit).
- A subject does not respond to the registered letter sent after the 3 attempted telephone contacts

9.0 Study Drug Administration and Management

Ivacaftor should be administered every 12 hours. It is recommended that subjects take ivacaftor approximately 30 minutes after the start of a meal or snack. Whenever possible subjects should take ivacaftor at the same time each day. On day 1 subjects who meet all inclusion and exclusion criteria will be enrolled in the study. In this study, all subjects will receive 150 mg ivacaftor BID or placebo. The research pharmacist will provide logs of investigation product and maintain those in a study binder.

9.1 Role of Vertex IIS regarding provision of study drug and placebo

- Vertex Pharmaceuticals will provide ivacaftor and matching placebo to randomize up to approximately 50 subjects to achieve approximately 40 completers (35 active patients and 15 placebo treated patients for 84 days, assuming 5 dropouts in the ivacaftor group and 5 dropouts in the placebo group). This will provide sufficient compound for lost samples, if they occur.

10.0 Packaging and Labeling

Ivacaftor will be supplied as a tablet for oral administration, film-coated, 150 mg. Drug and placebo will be provided from Vertex Pharmaceuticals.

11.0 Study Drug Supply, Storage and Handling

Ivacaftor tablets must be stored at room temperature, 15-30 degrees Celsius. While at the site, ivacaftor must be stored in a secure, temperature-monitored area of limited access. On day 1 a 28 day supply (+/-2 days) supply of ivacaftor will be dispensed to the subject. The drug will be dispensed an additional 28 day supply at day 28 and 56, with all drug being returned to the site at the day 84 visit.

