- Uncontrolled Diabetes
- Recent (e.g 1year) arterial thrombotic events (peripheral arterial disease, thrombotic stroke)
- Clinically significant arrhythmias requiring anti-arrhythmic agent(s) or conduction abnormalities that in the opinion of the investigator that affect patient safety such as the abnormalities listed below (patients with stable coronary artery disease are eligible)
 - ♦ Angina symptoms
 - ♦ History of MI
 - ♦ Revascularization procedure in the last year prior to screening
 - ♦ Clinically significant congestive heart failure (known LVEF $\leq 45\%$, cor pulmonale, diastolic heart failure, etc)

Investigational Drug: Ivacaftor, 150 mg PO every 12 hrs (or matching placebo)

Schedule of Study Visits: The first dose of ivacaftor will be administered at the Day 1 visit. Ivacaftor will be taken twice daily, with 12 hours between each dose from day 1 through the morning dose of day 84. Study visits will occur at Screening (-28 to -1 days), Day 1, Day 28 (\pm 7), Day 56 (\pm 7), Day 84 (\pm 7), and Follow-up (14 \pm 7 days after the last dose of ivacaftor).

Outcome Measures:

Safety assessments: Assessments include tests used in clinical studies to monitor the safety of ivacaftor in CF, including adverse event reporting, clinical laboratory testing, physical exams, and spirometry. The PI will review all SAEs in real time and conduct appropriate reporting to the FDA and IRB, as required, within 24hrs at maximum. Interim safety analysis will include review of AEs and safety labs by the PI and will be conducted after completion of approximately 10, 20, and 30 subjects. Ocular exam will be performed at baseline unless known history of cataracts.

PK: PK/PD analyses between ivacaftor levels and CFTR activity in the sweat gland will reveal new insights into the degree that wild-type CFTR can be activated. Calculated PK parameters include: area-under-the-curve (AUC₁₂), maximum plasma concentration (C_{max}), time to C_{max} (T_{max}), oral clearance (CL/F), terminal apparent distribution volume (V_z/F), and elimination half-life (t_{1/2}). Subsequently, intensive data and sparse plasma concentrations will be combined to create a population PK model to assess covariates, such as age, weight, sex, smoking status, etc. as previously conducted by our group for NIH and industry sponsored studies.

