4.0 STUDY DESIGN

The study is a Phase 2 Study to establish the safety and efficacy of the CFTR potentiator ivacaftor in patients with chronic obstructive pulmonary disease (COPD), chronic bronchitis, and acquired CFTR dysfunction as detected by sweat chloride analysis. The design is a pilot, randomized (3:1, active:placebo), double-blind, placebo-controlled study to determine the safety and efficacy of ivacaftor (VX-770) in approximately 40 subjects with COPD.

Enrollment is planned at our single center, The University of Alabama at Birmingham. Patients will be randomized 3:1 to active drug (n=30) and placebo (10) to achieve the enrollment goal.

- A sufficient number of subjects will be screened to randomize up to 50 subjects to achieve 40 completed subjects to receive either ivacaftor 150 mg BID (n=30) or placebo (n=10) for 84 days.
- The schedule of assessments is shown in Table 1. The protocol design is shown in Figure 1.
- Ivacaftor and matching placebo will be orally administered as capsules according to the following guidelines:
 - Between study visit Day 1 and study visit Day 84, subjects will take 1 dose of study drug each day in the morning, beginning any time between 08:00 h (8:00 AM) and 12:00 h (12:00 PM). Whenever possible, subjects should take the study drug at the same time each day.

- On the study visit days when PK samples are collected (study visit Days 1, 28, 56, and 84), the study drug is to be taken by the subject while he/she is at the study site
- For visits after the Day 1 visit, subjects will be instructed to bring all remaining study drug materials to the site; study drug will be dispensed at each visit.
- Ivacaftor will be prepared and dispensed by an unblinded pharmacist.
- Subjects will be instructed to continue their standard COPD medication regimen.

Table 1. Schedule of Assessments ^a8 hr PK (pre, 1, 2, 4, 8, hr samples). ^b peak and trough PK only, ^crandom PK, ^donly if indicated.

Assessment	Screen (Day -28 to -1) Visit 1	Day 1	Day 28 (± 2)	Day 56 (± 2)	Day 84 (± 2)	Follow Up (Day 98 ± 2)
		Visit 2	Visit 3	Visit 4	Visit 5	Visit 6
Informed Consent	X					
Medical History & Concomitant Medications	X	X	X	X	X	X
Physical Examination	X	X	X	X	X	X
Safety Labs	X		X	X	X	X ^d
CFTR Genotyping	X					
Urine Pregnancy Test		X	X	X	X	X
Serum Pregnancy Test	X					
Blood Biomarker Collection		X	X	X	X	X
Spirometry	X	X	X	X	X	X
Sweat Chloride	X	X	X	X	X	X
MCC	X				X	
Patient report outcome questionnaires		X	X	X	X	X

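### The visit window, last dose, drug supply and Table 1 disagree around Day 84, so the only post-baseline MCC and 6-minute walk could be measured off drug

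*Combined protocol and SAP*

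**What the plan says.** **Last dose.** Synopsis, Schedule of Study Visits: "Ivacaftor will be taken twice daily, with 12 hours between each dose from day 1 through the morning dose of day 84". Section 4.0 ties dosing to visits instead: "Between study visit Day 1 and study visit Day 84, subjects will take" study drug. (That sentence goes on to describe one morning dose a day, against every 12 hours elsewhere. This is a separate conflict and does not alter the day count below, because supply is stated in days.)

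**Visit window.** The synopsis gives 7 days either side for Days 28, 56 and 84, and places follow-up 14 days, give or take 7, after the last dose. Table 1 gives 2 days either side for the same visits and sets follow-up at Day 98, give or take 2.

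**Supply.** Section 11.0: "On day 1 a 28 day supply (+/-2 days) supply of ivacaftor will be dispensed to the subject". Two further supplies of 28 days each follow at Days 28 and 56, and subjects hand back whatever is left when they attend for Day 84. The two-day allowance is attached only to the Day 1 dispensing.

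**Leftover drug.** Section 4.0 has subjects bring what remains to each visit, where drug is dispensed. Section 12.0 keeps returned materials at the site, and Section 13.0 allows their destruction after accountability. No section says whether unused tablets are given back.

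**Dosing on Day 84.** Section 4.0 applies to days "when PK samples are collected (study visit Days 1, 28, 56, and 84), the study drug is to be taken by the subject" at the site. The Drug Administration row of Table 1 is marked at Days 1, 28 and 56 but not at Day 84, where peak and trough PK are scheduled.

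**Measurements.** Table 1 has MCC at Screening and Day 84 only, the 6-minute walk at Day 1 and Day 84 only, and spirometry at every visit. Section 6.0 tests the within-group change from screening/Day 1 to Day 84 with a paired test. It assesses the off-drug effect from Day 84 to follow-up.

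**The concern.** A site that follows the synopsis window and the Section 11.0 quantities can see a patient for the Day 84 visit after the tablets have run out. Nothing else measured on treatment could replace that patient's MCC or 6-minute walk. The Day 84 FEV1 would enter the paired test as if on drug, and the Day 84 peak and trough, part of a primary endpoint, would not describe continued dosing. Section 6.0 has no rule for such values.

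The washout contrast is exposed too. If the last dose is on Day 84, the synopsis follow-up window opens on the last day on which the synopsis permits the Day 84 visit. Both ends of the contrast could then be off drug for the measures taken at both visits (spirometry, sweat chloride, questionnaires).

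**Working it through.** **1. Planned duration.** Section 9.1 plans 84 days of treatment. Supply on the literal wording is 28 + 28 + 28 = 84 days, so the plan's figure is reproduced. At two doses a day this is 168 doses. Day 1 through the morning of Day 84 needs 83 × 2 + 1 = 167. With two extra days on Day 1 the total is 86 days; with two fewer it is 82.

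**2. Latest visit.** Synopsis: 84 + 7 = Day 91. Table 1: 84 + 2 = Day 86.

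**3. Gap.** Full drug-free days = visit day − last covered day − 1. If leftovers are kept and dispensing is on time, the last covered day is the total supply in days. If they are not re-issued, it is the Day 56 dispensing date + 27.

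| Window | Leftovers | Day 56 visit held on | Last covered day | Day 84 visit held on | Full drug-free days |
|---|---|---|---|---|---|
| Synopsis | kept | Day 56 | 84 | 91 | 6 |
| Synopsis | kept, +2 on Day 1 | Day 56 | 86 | 91 | 4 |
| Synopsis | not re-issued | Day 56 | 83 | 91 | 7 |
| Synopsis | not re-issued | Day 49 | 76 | 91 | 14 |
| Synopsis | either | Day 63 | 90 | 91 | 0 |
| Table 1 | kept | Day 56 | 84 | 86 | 1 |
| Table 1 | kept, +2 on Day 1 | Day 56 | 86 | 86 | 0 |
| Table 1 | not re-issued | Day 54 | 81 | 86 | 4 |

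In the first two rows the visit falls 91 − 84 = 7 or 91 − 86 = 5 days after the last covered day. In the Day 63 row the gap only moves earlier: with the Day 28 visit on time and leftovers kept, the first two dispensings cover 56 days, leaving Days 57 to 62 uncovered.

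**4. Follow-up overlap.** Last dose on Day 84 plus 14 − 7 = 7 days gives Day 91, the latest Day 84 visit under the synopsis. Table 1's follow-up (Days 96 to 100) does not overlap its own Day 84 window (Days 82 to 86).

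**5. Illustration of dilution, on assumed inputs.** Table 2 uses a two-sided paired t-test, n = 27, α = 0.05. Power comes from the noncentral t with 26 degrees of freedom and noncentrality δ/(SD/√27).
- MCC: 3.9/(7/√27) = 3.9/1.347 = 2.895, power 79.6%.
- FEV1: 2.8/(5/√27) = 2.8/0.962 = 2.910, power 80.0%.

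Both reproduce the stated 80%. Now assume that a fraction f of active patients is measured off drug with complete loss of effect and that the SD is unchanged, so that δ becomes δ(1 − f).

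| f | MCC δ | MCC power | FEV1 δ | FEV1 power |
|---|---|---|---|---|
| 10% | 3.51 | 70.8% | 2.52 | 71.3% |
| 20% | 3.12 | 60.6% | 2.24 | 61.1% |
| 30% | 2.73 | 49.7% | 1.96 | 50.1% |

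The documents give neither f nor the rate at which the effect is lost.

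**The case against.** The intention was plainly to measure on drug. Section 4.0 runs dosing to the study visit and has that day's dose taken at the site, and day 84 in the synopsis may be a visit label rather than a calendar day. The two-day allowance in Section 11.0 matches Table 1's window, so the root may be one discrepant window in the synopsis. With leftovers kept, Table 1's window leaves at most one full drug-free day. Day 91 is the outer edge of the wider window. FEV1 is also measured at Days 28 and 56, and Section 6.0 plans repeated-measures mixed models. The primary endpoints of this pilot are safety and PK.

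Most of this stands as a limit on size. It does not remove the conflict. The stated quantities do not sustain dosing to Day 91 on the literal reading with on-time dispensing, whatever the intention. Choosing Table 1's window is not enough by itself either: if leftovers are not re-issued, a gap of up to 4 full days remains inside it. The earlier FEV1 values do not enter the paired test to Day 84, and MCC and the 6-minute walk have no earlier on-treatment value.

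A reader might infer that 28 to 30 days are issued at every visit, so that a gap of 5 to 7 days at Day 91 is fixed. The text does not support this. The allowance is given for Day 1 only, and if two extra days were issued all three times and leftovers kept, supply would be 3 × 30 = 90 days, with no full drug-free day before Day 91.

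**Conclusion.** The contradiction is real and should be fixed. On the literal supply, with on-time dispensing and leftovers kept, a Day 91 visit falls 5 to 7 days after the last covered day (4 to 6 full drug-free days). This range takes the Day 1 allowance as zero to plus two days. Across permitted visit dates and both readings on leftovers, the gap before the latest visit runs from none to 14 full days under the synopsis and from none to 4 under Table 1. For a patient with such a gap, MCC, the 6-minute walk, the Day 84 FEV1 in the paired test and the Day 84 PK would be off drug. The washout contrast could collapse only at the Day 91 edge, and only if the last dose is on calendar day 84.

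A reader might go further and infer that Day 84 results will generally be off drug, or that power will fall to 50 to 70%. The documents do not support either. They give no distribution of visit dates and no offset rate, so the bias cannot be computed. The power figures show only what an assumed fraction with complete loss of effect would cost.

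**What to change.** Reconcile the synopsis visit schedule, Section 4.0 with Table 1, Section 11.0 and Section 12.0 so that five items agree: the visit window, the last dose, the dispensed supply, the handling of leftover drug, and the Day 84 cell of the Drug Administration row. Which rule to keep is for the sponsor to decide.

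Record the date and time of the last dose at each efficacy and PK assessment. Pre-specify in Section 6.0 a supporting analysis that treats Day 84 values taken after a dosing gap as off drug, and define such a gap beforehand.

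The cost is protocol wording, one data field if it is not already collected, and one extra analysis. No added visits or patients are needed.
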